Primary Aim: The primary outcome is the change in abdominal obesity operationalized as MRI-determined visceral adipose tissue (VAT). Over the course of a 2-year period and working collaboratively with a real workplace, **WorkACTIVE-P** will randomly assign 41 low active (< 7,500 steps/day), overweight/obese sedentary full-time workers (reporting "mostly sitting" during the work day), 18-64 years of age, with abdominal obesity defined by waist circumference and at least one additional component of the metabolic syndrome (dyslipidemia, elevated blood pressure, and/or impaired fasting glucose¹²), to a 3-month-long controlled trial. The trial will include baseline and 3 month assessments and two intervention arms: 1) a combined electronic behavior support program of "walk more and pedal desk" (WMPD, n=20), which, in addition to provision of a dedicated pedal desk in individual worker's office space, participants are supported to increase daily walking by at least 3000 steps/day; and 2) a no-intervention control condition (CON, n=20). This design allows us to test the hypothesis that: this innovative multi-component workplace energy expenditure intervention will elicit measureable improvements in abdominal obesity superior to the control condition. Relative contributions of the two intervention components (walk more and pedal desk) will be determined by regression analyses predicting VAT changes.

Additional Aims: Secondary outcomes include changes in body weight, total adipose tissue, subcutaneous adipose tissue, blood pressure, blood lipids, fasting glucose and insulin, [HbA1c], free-living accelerometer-determined walking (steps/day and cadence), time spent in sedentary behavior, exercise (time spent at moderate-to-vigorous physical activity), and dietary intake. We will electronically track daily steps data for WMPD participants and also duration of use and cadence (revolutions per minute, or RPM) of dedicated pedal desks. After completion of this pilot study, a subsequent R01 will be proposed to perform a full-scale RCT to quantify the separate and combined effects of the intervention components on change in the study endpoints.

III. Overview of Research Design

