The purpose of the WorkACTIVE-P study is to assess the outcome of an innovative multi-component intervention focused on increasing energy expenditure and re-balancing the disrupted energy balance equation of sedentary workplaces with an ultimate target of reducing workers' abdominal obesity. The primary outcome is MRI-determined visceral adipose tissue (VAT), which is an indicator of abdominal obesity. Secondary outcomes include changes in body weight, total adipose tissue, subcutaneous adipose tissue, blood pressure, blood lipids, fasting glucose and insulin, HbA1-c, free-living accelerometer-determined walking, time spent in sedentary behavior, exercise, and dietary intake.

Table 1 describes the timeline of activities during the 2 year trial period for **WorkACTIVE-P**.

Activity	Year 1				Year 2			
	1	2	3	4	1	2	3	4
MOP development, procedures training								
Recruitment & screening								
Writing design & methods paper								
Baseline testing & randomization								
3-month testing								
Data cleaning & management								
Data analysis & interpretation								
Paper writing & submission								

IV. Study Population

The target study group will be up to 41 sedentary men and women aged 18 to 64 years. Because potential participants will be overweight and obese individuals, the study sample will be at risk for negative health conditions associated with excess adiposity, including cardiovascular disease (CVD). Consequently, the same will be representative of individuals who have a sedentary job and are likely to be prescribed exercise regimens.

Table 2. Criteria for Study Participation

Inclusion Criteria	
Gender	Both men and women.
Age	18-64 years.
BMI	BMI $\geq 25 \text{ kg/m}^2$
Waist circumference alone OR two or more of the remaining four risk factors defining metabolic syndrome ¹²	
 Waist circumference $\geq 102 \text{ cm}$ (men) or $\geq 88 \text{ cm}$ (women) Triglycerides $\geq 150 \text{ mg/dL}$ or currently prescribed and taking anti-hyperlipidemic medications HDL cholesterol $< 40 \text{ mg/dL}$ (men) or $< 50 \text{ mg/dL}$ (women) or currently prescribed and taking anti-hyperlipidemic medications Resting systolic blood pressure $\geq 130 \text{ mm Hg}$ or diastolic $\geq 85 \text{ mm Hg}$ or currently prescribed and taking anti-hypertensive medications Fasting glucose $\geq 100 \text{ mg/dL}$³⁴

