Rationale for inclusion/exclusion criteria: Since this is a real world implementation the gender breakdown will reflect the makeup and preferences of the targeted office-based workplace. Ages 18-64 were chosen since these are the ages that increase our likelihood of targeting metabolic syndrome. This will reduce the costs of screen fails in this pilot study. We anticipate that we will expand the age range to include younger people with metabolic syndrome in a future R01 study.

V. Recruitment

Since we are primarily targeting workers from a local, large corporation (Blue Cross Blue Shield, Baton Rouge, LA) that Pennington Biomedical has previously worked with to conduct a randomized controlled trial of a treadmill desk intervention, we will be using specially tailored recruitment strategies based on this earlier direct experience. During the study startup phase, members of our research team will attend face-to-face meetings with key members of the company's staff including facilities directors, human resources representatives, information technologists, department supervisors, and wellness coordinators. If required, we will also attend a supervisors' meeting to present information about the planned study, including who will be eligible, time and space requirements, and other expectations. Email and telephone communication will also prepare the company for the study recruitment and implementation. We will also recruit from Pennington Biomedical Research Center, Louisiana State University, LA Office of Technology, LA Healthcare Connections, Entergy, and LA Community and Technical College System in order to supplement enrollment. All companies will follow similar recruitment strategies and processes if deemed appropriate by the site.

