If more than 16 days lapse between SV and Baseline scheduled date, participants may be asked to repeat measures to re-assess eligibility.

Baseline Visit:

Eligible participants after SV1 will return to Pennington Biomedical Research Center approximately one week but up to 16 days after SV1 for a Baseline Visit. Participants will return the accelerometer to further evaluate each participant's ability to comply with the wearing requirement of objectively monitored devices (i.e., at least 4 days with at least 10 hours of wear time recorded), allowing us to exclude participants with poor adherence to study requirements. Accelerometer data (physical activity and sedentary behavior) obtained during this screening process will serve as participants' baseline accelerometry data. An MRI will be completed to collect visceral fat, subcutaneous fat, and muscle compartments. Female participants will have a urine pregnancy test before the MRI. Randomization will occur at the conclusion of the Baseline Visit. Using a computerized pseudo-random number

generator, the study statistician will determine the randomization order in advance. The participants will be enrolled as directed by the next assignment letter contained in a randomized sequence of sealed and numbered envelopes. The project manager or interventionist (i.e., unblinded staff member) will reveal the randomization assignment to the participant. The participant will be provided with a behavioral expectations document informing them of the expectations of their randomized group. Study assessment staff will remain blinded to a participant's study arm allocation.

Month 3 Follow Up:

Randomized participants will return to Pennington Biomedical Research Center for a Follow-Up Visit approximately 3 months after intervention starts. Participants will return an accelerometer that was provided to them 1 week prior at their work place. Participants will complete questionnaires related to physical activity. All measures collected at the Screening and Baseline Visits will be repeated (blood work, body measurements, MRI, and RFPM). Female participants will have a urine pregnancy test prior to the MRI.

a. Description of Tests and Procedures:

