This is a study of an innovative multi-component intervention delivered in a real workplace. The primary outcome is change in VAT. The sample sizes herein were set based on data collected in our Pounds Lost51 study that showed baseline VAT to be approximately 5.43 kg and indicated that a 21% reduction in VAT (equivalent to 1.15 kg, SD=1.20kg) can be achieved with a suitable intervention. The nominal level of significance alpha = 0.05 will be used to compare mean VAT change (e.g., reduction) in WMPD vs CON, A minimum of 18 subjects per intervention who all complete protocol through end of study would conservatively provide at least 80% power for detecting significance where the underlying true differential intervention change in VAT is at least 1.15 kg. We have planned for 20 participants per group (total n = 41) in this study to allow for 10% attrition. As designed, this study will clearly inform the feasibility of combining these components of a workplace multi-component energy expenditure intervention.

b. Data Management:

The data management will be conducted by the Pennington Biomedical Research Computing Group. There will be limited access to all data including locked cabinets for paper files and password protected computers for electronic data. The PBRC has a fully integrated, campus-wide, automated, data management system. All data are entered into a Central Database using existing methodology that has been fully validated and undergoes continuous quality assurance by the PBRC Research Computing Core and NORC. Most data are automatically uploaded from the instruments that measure the endpoint. All self-report inventories will be scanned and scored automatically using the Psychological Assessment Laboratory's optical scanning system, which automatically uploads the data into the Central Database. Exercise testing data will be downloaded from the Parvo Medics' TrueOne® 2400 cart directly following each test and reviewed for integrity. All data are backed-up daily and the Research Computing Core at the PBRC oversees all data management.

c. REDCap Database:

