On study change in MRI-determined VAT, weight, waist circumference, fasting glucose and insulin, HOMA-IR will be summarized by intervention group as means and 95% confidence intervals in an intention-to-treat analysis of (1) all participants and (2) the subset of participants who achieve the highest tertile of adherence to the intervention. Linear models will provide the primary framework for significance testing. In the analysis of VAT (the primary outcome), statistical significance of differential longitudinal changes in response to intervention (WMPD vs CON) will be assessed employing repeated measures mixed effects models with maximum likelihood estimation and Kenward-Rogers adjustment to the degrees of freedom in an intention-to-treat analysis of (1) and (2) for each outcome measure using all available data. Study arm (WMPD. or CON), age, race, sex and interactions will be taken as having fixed effects; participants within groups will be considered as having random effects. Covariates such as age, sex, race and baseline assessment of VAT will be included in preliminary models and retained in final analytic models if warranted. The model residual covariance structure (e.g., unstructured, compound symmetric, auto-regressive) across time will be investigated to enhance efficiency of statistical tests. Secondary outcomes, such as on-study changes in weight, waist circumference, fasting glucose, insulin, and HOMA_IR will be analyzed using statistical models analogously to the approach described for the primary outcome.] Results for each outcome will be summarized as least squares means and 95% confidence intervals for each intervention across the assessment times. Model residuals will be tested to see if they have distributions that are approximately Gaussian and data transformations will be performed if needed. Group differences in baseline characteristics will be tested and corrective steps, such as post-stratification and adding model covariates will be employed as necessary Null hypotheses will be tested against two-directional alternatives at the nominal 0.05 significance level using Bonferroni adjusted p-values when appropriate. All statistical analyses will be performed using statistical software in SAS version 9.3.

X. References

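### The plan gives 20 participants per group but a total of 41, and states no allocation restriction that would secure 20 per arm; the power at stake is small

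*Combined protocol and SAP*

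**What the plan says.** Section IX.a (Sample size and statistical power) sets the requirement: "A minimum of 18 subjects per intervention who all complete protocol through end of study would conservatively provide at least 80% power". It then gives the enrolment plan: "We have planned for 20 participants per group (total n = 41) in this study to allow for 10% attrition".

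Three other places give a size:

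- The opening purpose paragraph, before section II, has 41 people recruited and randomised.
- Section II.b (Primary Aims and Hypotheses) also randomises 41, but gives the intervention arm as n=20 and the other arm as "a no-intervention control condition (CON, n=20").
- Section IV (Study Population) treats the number as a ceiling: "The target study group will be up to 41 sedentary men and women".

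Allocation is described once, under Baseline Visit in section VI. A computerised pseudo-random number generator is used, and "the study statistician will determine the randomization order in advance"; assignments are held in sealed, numbered envelopes. Section VII adds only that there are two arms. No section states an allocation ratio, blocks, strata, minimisation or a cap per arm.

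**The concern.** The total and the per-group figure cannot both hold, and the conflict sits in the sample-size section and the primary aim, where a reader looks for the definitive number. Calling 41 a ceiling in section IV leaves it unclear whether the target is 40, 41 or something lower.

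The per-arm number matters because the attrition allowance uses all of it: 20 less 10% is exactly the 18 completers that the power statement needs. Envelopes filled from a list fixed in advance conceal the next assignment, but they do not balance the arms. Unless the list is restricted in some way, 20 per arm is an expectation and not something the procedure delivers. At stake are a clear enrolment target, a reproducible description of the randomisation, and a modest amount of power.

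**Working it through.** **Inputs.** From section IX.a: difference in visceral adipose tissue (VAT) change 1.15 kg, SD 1.20 kg, alpha 0.05 ("The nominal level of significance alpha = 0.05 will be used to compare mean VAT change"), power 80%, attrition 10%. From section IX.d: two-sided testing ("Null hypotheses will be tested against two-directional alternatives at the nominal 0.05 significance level").

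**Step 1: reproduce the per-arm figures.** Normal approximation, with z values 1.960 and 0.842:

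n per arm = 2 × (1.960 + 0.842)² × 1.20² / 1.15² = 2 × 7.849 × 1.44 / 1.3225 = 17.1, rounded up to 18.

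Inflation for attrition: 18 / 0.9 = 20 per arm. Both match the plan.

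**Step 2: the total.** 20 + 20 = 40, not 41. The surplus of one is in the safe direction.

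**Step 3: slack at 18 per arm.** The standardised difference is 1.15 / (1.20 × √(2/18)) = 2.875. The normal approximation gives Φ(2.875 − 1.960) = 82.0%. The two-sided t test, using the noncentral t with 34 degrees of freedom, gives 79.8%. So the claim of at least 80% holds by the normal approximation and is just missed by the t test.

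**Step 4: how far the arms could drift.** This step assumes an unrestricted 1:1 list, which the plan neither states nor rules out. The size of one arm is then Binomial(41, 0.5):

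- smaller arm fewer than 20: 75.5%
- smaller arm fewer than 18, before any dropout: 34.9%
- smaller arm fewer than 14: 2.8%
- the central 95% of splits extends to 14:27

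**Step 5: convert arm sizes to power.** Noncentral t, two-sided 0.05, with the standardised difference 1.15 / (1.20 × √(1/n₁ + 1/n₂)). For the last column each arm is multiplied by 0.9.

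| Split | Power, no attrition | Power after 10% attrition |
|---|---|---|
| 20:20 (total 40) | 84.0% | 79.8% |
| 20:21 | 84.9% | 80.8% |
| 17:24 | 83.8% | 79.6% |
| 16:25 | 83.1% | 78.8% |
| 14:27 | 81.0% | 76.5% |
| 13:28 | 79.5% | 75.0% |

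Averaged over all binomial splits of 41, power after 10% attrition is 79.8%. That is 1.0 point below a fixed 20:21 and equal to the plan's own 18 per arm. At 14:27 the loss against 20:21 is 80.8 − 76.5 = 4.3 points.

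**The case against.** The strongest reply is that silence about restriction is not evidence of simple randomisation. A list drawn up in advance by a statistician, for a trial with stated targets of 20 per arm, could well be blocked, or could be a shuffled list of fixed length. The text fits those as well as it fits an unrestricted sequence. This stands: the 76% and 35% are conditional, and the point is a gap in the description, not a demonstrated flaw in the list.

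A reader might take the 35% as the chance that the trial is underpowered. The plan's inputs do not support that. Power depends on both arms, and a small arm in a trial of 41 is partly offset by a large one. Before dropout, power falls below 80% only when the smaller arm is under 14, which has probability 2.8% even with an unrestricted list.

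A reader might also infer that the sample size itself is wrong. It is not: 18 and 20 both reproduce, and 41 exceeds 40. What fails is the agreement between the per-group figure and the total.

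Finally, a reader might infer that stratifying by sex is required, because the waist entry limits differ by sex and "the gender breakdown will reflect the makeup and preferences of the targeted office-based workplace". With a fixed 20:21 split, the share of men would differ between arms by at least 20 percentage points in 13% to 22% of trials, on an assumed 8 to 20 men among 41. But the plan gives no sex mix, differing entry limits do not show that sex predicts VAT change, and section IX.d already lists sex as a fixed effect. That section also describes sex as a covariate kept only if warranted. This is a reason to fix its place in the model, not a reason to require stratification.

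**Conclusion.** The concern holds as an inconsistency in the stated sample size together with an incomplete allocation description. That 20 per group and a total of 41 disagree is certain and needs no assumption. That no ratio or restriction is stated is also certain; whether the list is in fact unrestricted is unknown.

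The practical effect is small. If the list is unrestricted, power after 10% attrition is about 1 point lower on average than with 20:21, and about 4 points lower at 14:27. These figures rest on the plan's 1.15 kg difference and 1.20 kg SD, equal attrition in both arms, and a two-sample t test standing in for the mixed model. The point is worth correcting because the plan has no margin above its 18 completers per arm and the correction is cheap, not because power collapses.

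**What to change.** 1. Choose one total and use it in the opening purpose paragraph and in sections II.b, IV and IX.a: either 41 randomised as 20 and 21, naming which arm has 21 or saying that the list decides, or 40 randomised as 20 and 20.
2. In section VI, Baseline Visit, state 1:1 allocation in permuted blocks of varying size, with block sizes withheld from the staff who open the envelopes. If the existing list is already restricted, one sentence describing it is enough. If it is not, apply the blocked list to participants not yet randomised.
3. In section IX.d, keep sex in the analysis model as a prespecified covariate, not one retained only if warranted.
4. Optionally, stratify the blocks by sex. The downside is two envelope series instead of one.

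The cost is a wording change and, only if the present list is unrestricted, a new set of envelopes for the remaining participants.

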- **Dietary Intake:** Food intake data will be captured with the Remote Food Photography Method (RFPM) using participants' personal (or one of our loaned) smartphones. The RFPM and SmartIntake© app (previously developed and validated by study Principal Investigator, [name] and colleagues^{38,39}) will be used to collect energy and nutrient intake data at baseline and month 3. Participants will use the procedure to photograph and track their dietary intake for 7 consecutive days, with the first 1-2 days being a run-in period to acclimate participants to the procedure, resulting in approximately 4-5 complete days of data per participant. Three days of recorded food intake has been shown in several studies to provide an accurate estimate of average food intake;⁴⁰⁻⁴² hence, we are collecting ample data to obtain a representative sample of habitual food intake.
- **Height and weight:** Height and weight will be measured to the nearest 0.1 kg using a standard stadiometer and balance beam scale, according to Pennington Biomedical's SOP.
- **MRI-determined visceral adipose tissue (VAT; indicator of abdominal obesity):** Magnetic resonance imaging (MRI) will be performed using a 3.0 T scanner (General Electric, Discovery 750w System, Milwaukee, WI). Subjects will in a supine position on the scanner table with the arms above the head. Subcutaneous fat, visceral fat, and muscle compartments will be traced on each slice by a trained analyst using Analyze™ software (AnalyzeDirect, Overland Park, KS) and a standardized tracing protocol.
- **Step-counter:** Participants will be instructed to wear the NL-1000 pedometer or a similar model at their waist for seven consecutive days. Fitbit Zip© devices may be worn in place of the pedometer during the Run-In period as needed.
- **Waist circumference:** Waist circumference will be taken according to Pennington Biomedical's SOP and measured to the nearest 0.1 cm.

VII. Interventions

Participants will be randomized into 1 of 2 intervention arms: Usual Working Condition Control group (UWC) or a combined intervention of Walk More and Pedal Desk (WMPD).

- a. **Usual Working Condition Group (UWC):** The no-intervention control condition will be asked to maintain their usual work and lifestyle throughout the study. Participants may be contacted by Pennington Biomedical staff during the intervention.

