c. **Adherence:** The importance of completing the expected intervention will be reinforced at every opportunity. A concern is that some participants may fail to complete their time on the pedal desk as well as complete the extra 3,000 steps per day. Prior to randomization, participants will have completed an extensive screening process, including the run-in, which we have found promotes adherence and excludes potential participants who cannot commit to the study. Participants will also be given a study expectations page for their intervention. If a participant misses a day on the pedal desk, his/her interventionist will contact them to check in, encourage attendance, and help problem-solve if a barrier to participation is present. These staff will be trained by [name], a licensed Clinical Psychologist, in behavioral strategies to promote adherence, and [name] will be available for consultation regarding challenging participants. The exercise laboratory will be open 5 days per week for 12.5 hours/day to accommodate a variety of schedules.

We recognize that it is unrealistic to expect 100% adherence to the intervention protocol. Participants may miss work due to illness or family obligations or have vacations planned. Therefore, we are defining acceptable compliance to the study protocol as completing 75% or more of the total amount of sessions prescribed. This will be defined as attended sessions per week on the pedal desk divided by expected sessions per week. In addition, steps per day will be used to calculate total adherence by dividing completed steps per day by expected steps per day. An average of the two compliance and adherence numbers will be used for the participant’s total adherence.

d. **Dropouts:** We define dropout as failing to return for the 3-month examination. We believe the run-in and screening visit will exclude many at high risk of dropout. Personalization and problem solving approaches to ensure adherence to exercise also will be helpful in preventing dropout.

e. **Participant incentives:** We will provide \$200 per individual as a compensation stipend for participation in the study regardless of group assignment. Enrolled participants (control or WMPD group) will receive \$100 for completing baseline and another \$100 for completing follow-up clinic visits held at the Pennington Biomedical clinic for a total of \$200.

VIII. Participant Safety and Confidentiality

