REDCap, a web-based application used to build and manage surveys and databases, will be used for questionnaire collection in this study. REDCap (Research Electronic Data Capture) is a secure, web-based application that is flexible enough to be used for a variety of types of research. REDCap provides an intuitive user interface that streamlines project development and improves data entry through real-time validation rules (with automated data type and range checks). REDCap also provides easy data manipulation (with audit trails for reporting, monitoring and querying patient records) and an automated export mechanism to common statistical packages (SPSS, SAS, Stata, R/S-Plus).

In addition to traditional data capture functionality, REDCap's survey capabilities are a powerful tool for building and managing online surveys. The research team can create and design surveys in a web browser and engage potential respondents using a variety of notification methods. All data collection projects rely on a thorough, study-specific data dictionary, defined by all members of the research team in an iterative, self-documenting process. This iterative development and testing process results in a well-planned and individualized data collection strategy. Pennington Biomedical has a license agreement with Vanderbilt and the database and software are installed on our local servers and hosted by Pennington Biomedical, not by Vanderbilt. The Vanderbilt University Office of Research will not be used as a central location for data processing and management. That is all done by Computing Services and RCG staff at PBRC. More information about the consortium is available at <http://www.project-redcap.org/>.

d. Data Analysis:

Baseline participant characteristics (e.g., age sex, race, weight, BMI, fasting glucose insulin, and HOMA-IR) will be summarized by intervention group as counts and percentages for categorical variables, and means and 95% confidence intervals for continuous variables. Adherence to protocol assessments (e.g., daily steps, minutes accrued on the pedal desk, rpm on the pedal desk) will be summarized similarly by week for each intervention.

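### The between-arm test in the highest adherence tertile is called intention-to-treat, but it selects on post-randomisation behaviour that has no score in the control arm

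*Combined protocol and SAP*

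**What the plan says.** Section IX.d names two analysis sets under one label: "intention-to-treat analysis of (1) all participants and (2) the subset of participants who achieve the highest tertile of adherence to the intervention". It then specifies the test of differential VAT change between WMPD and CON by repeated measures mixed model, "in an intention-to-treat analysis of (1) and (2) for each outcome measure using all available data". Secondary outcomes are to be analysed in the same way. No sentence ranks the tertile set below the full set or calls it exploratory.

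The only adherence score is in section VII.c. The pedal-desk part is "defined as attended sessions per week on the pedal desk divided by expected sessions per week". The step part comes from "dividing completed steps per day by expected steps per day". The two are averaged. Section IX.d also lists what will be summarised: "Adherence to protocol assessments (e.g., daily steps, minutes accrued on the pedal desk, rpm on the pedal desk".

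On the control arm, section VII.a says: "The no-intervention control condition will be asked to maintain their usual work and lifestyle throughout the study". Table 3 gives the Fitbit and the pedal desk to WMPD only, and section II.b says: "We will electronically track daily steps data for WMPD participants and also duration of use and cadence". Randomisation takes place at the end of the Baseline Visit (section VI), before any of this adherence is recorded.

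**The concern.** An intention-to-treat comparison keeps participants in the groups that randomisation formed. A subset chosen by how well people followed the intervention does not. Participants who reach the top third may also differ in motivation, health, workload or home circumstances, and any of these may relate to VAT change. Section VII.c itself lists illness, family obligations and vacations as reasons for missed sessions, so non-adherence is unlikely to be random.

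There is also a gap in definition. A control participant has no desk sessions to attend and no step target to meet, so the score has no denominator in that arm. The text does not say whether the tertile is cut within WMPD or across both arms, or which controls form the comparator. That choice could be made after the data are seen.

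At stake is how the result is presented. A p-value from about six or seven adherent WMPD participants could be reported as intention-to-treat evidence, and so as protected by randomisation, in a pilot meant to support a later full-scale trial.

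**Working it through.** **1. The plan's own figure.** Section IX.a gives a difference of 1.15 kg, SD 1.20 kg, alpha 0.05 and 80% power. Section IX.d makes the tests two-sided.

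n per arm = 2 × (1.960 + 0.842)² × (1.20 / 1.15)² = 17.1, rounded up to 18. Allowing for 10% attrition, 18 / 0.90 = 20 per arm. Both figures reproduce. They cover all completers, not a tertile.

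**2. What the tertile set could mean.**

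| Reading | Result |
|---|---|
| Top third of WMPD against all CON | Can be carried out, but is not a randomised comparison |
| Tertile cut across both arms | Controls have no score |
| Separate top third within CON | No definition exists |

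Only the first reading can be run with the data described. It is used below as an assumption, because the plan does not state it.

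**3. Size of the subset.** 20 / 3 is about 7 randomised, and 18 / 3 = 6 completers. For the design effect of 1.15 kg, noncentral-t power is 56% for 7 versus 20 and 49% for 6 versus 18. By the same method it is 79.8% for 18 versus 18.

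**4. Bias with no treatment effect.** Let r be the correlation between adherence and VAT loss arising from causes other than treatment. The documents give no value for r, so it is varied. The expected spurious difference is

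bias = r × SD × (mean standard normal score of the selected third).

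That mean score is about 1.016 for the top 7 of 20 and 1.042 for the top 6 of 18. For r = 0.3:
- 7 versus 20: 0.3 × 1.20 × 1.016 = 0.37 kg
- 6 versus 18: 0.3 × 1.20 × 1.042 = 0.38 kg

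**5. Type I error.** This was simulated with 200,000 trials per cell, no treatment effect, SD 1.20 kg and a two-sided pooled t-test without covariates.

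| r | 7 vs 20: bias (kg) | Type I | Type I at 0.025 | 6 vs 18: bias (kg) | Type I | Type I at 0.025 |
|---|---|---|---|---|---|---|
| 0 | 0.00 | 5.1% | 2.5% | 0.00 | 5.0% | 2.4% |
| 0.2 | 0.24 | 7.2% | 3.9% | 0.25 | 7.0% | 3.8% |
| 0.3 | 0.37 | 10.2% | 5.7% | 0.38 | 9.5% | 5.5% |
| 0.5 | 0.61 | 20.0% | 12.8% | 0.62 | 18.4% | 11.4% |

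At r = 0.1 the bias is 0.12 kg and the type I error about 5.5% in both cases. The all-participants test stays between 4.9% and 5.1% in every cell. The 0.025 columns assume that Bonferroni is split over the two sets. The rejection rate still exceeds 2.5% whenever r is above zero, because the adjustment deals with multiplicity and not with selection.

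**6. Scale.** At r = 0.3 the artefact is 0.37 / 1.15 = 0.32, about one third of the design effect.

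**The case against.** The strongest reply is that this is a labelling slip in a pilot, and that the intended comparison is clear enough: adherence to the intervention can only mean WMPD, so the set is the top third of WMPD against all controls. That is the natural reading. It is still unwritten, though, and it remains a non-randomised comparison under an intention-to-treat label.

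Second, the documents point towards the full set as primary. The power calculation has no tertile in it, and the stated hypothesis concerns the intervention as a whole against control. This is fair as inference, but section IX.d does not say so.

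Third, controls do supply some data. Both arms have 7-day accelerometry at baseline and month 3, and every participant receives a document on the expectations of the assigned group. This yields a control step count, but no score against a step or pedal-desk target.

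Fourth, the illustration depends on an assumed r, and its sign is not established: r = −0.3 would give a bias of about −0.37 kg, against the intervention. It also leaves out the planned covariates. If one measured covariate carried the whole correlation, adjusting for it would remove nearly all the bias. Both points stand as limits on the size. However, age, sex, race and baseline VAT are kept only if judged warranted, and they cannot be assumed to capture motivation or circumstances.

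Last, one could keep the between-arm comparison, relabelled as an exploratory per-protocol analysis with its comparator rule stated. That would cure the label and the missing definition, but not the selection. Describing adherence within WMPD is also confounded, but it does not look like a randomised contrast.

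**Conclusion.** The concern holds. Section IX.d is wrong as written in calling the adherence-tertile set intention-to-treat, and it leaves the comparator undefined. Both defects stand whatever the value of r.

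The size of any bias is not known from the documents. The figures above are an unadjusted illustration that assumes the top third of WMPD is compared with all controls. On that basis, r from 0 to 0.5 gives a spurious benefit of 0 to about 0.6 kg and a type I error of 5% to about 20%, with no bias at r = 0.

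The all-participants analysis is specified and unaffected, so the trial's main test stands. This should be fixed, but it does not undermine the design.

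**What to change.** In section IX.d:

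- State that the analysis of all randomised participants is the only intention-to-treat analysis and the only confirmatory test of VAT.
- Remove the intention-to-treat label and the WMPD-versus-CON p-value from the tertile set, for VAT and for the secondary outcomes.
- Report VAT change by adherence score within WMPD only, as an exploratory description that is stated to be confounded. Place it beside the component analyses in section II.b, where relative contributions "will be determined by regression analyses predicting VAT changes".
- Do not replace the tertile comparison with a complier-average effect based on the same cut. WMPD participants below the cut also receive the desk, the Fitbit and the coaching (section VII.b), so they cannot be treated as unexposed.

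The cost is a few sentences, with no new data and no new model. The sponsor gives up a subset p-value that might have been favourable and keeps the descriptive information on adherence.
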